8.1.3 Adverse Events

Analyses of AEs will be based on the SAF set. AEs will be coded according to CTCAE v5.0 (for severity) and the Medical Dictionary for Regulatory Activities (MedDRA).

The total number/incidence of AEs will be summarized, including the number of subjects with at least one AE and the number of unique AEs per cohort and overall. The number of AEs per

severity (CTCAE) and relation to trial drug will also be included and summarized per cohort and overall. Additionally, listings of AEs leading to treatment discontinuation, resulting in death, and according to maximum severity will be tabulated. The incidence DLT/TLTs will also be evaluated for each dose level, and for all subjects combined. SAEs will be summarized in a similar manner.

The number of subjects and the number of AEs will be tabulated by MedDRA system organ class and preferred term. AEs will also be tabulated versus worst severity and worst relationship to treatment. In this table, subjects with AEs will be identified by their subject number.

Vital signs and body weight, 12-lead ECG parameters, laboratory data (hematology, biochemistry, coagulation, urinalysis) will be summarized using descriptive statistics. Shift tables showing changes from baseline will be generated where appropriate.

Pre-treatment events occurring between first assessment at screening and first dose of CyPep-1 will be summarized separately.

8.1.4 Efficacy Analyses

The efficacy endpoints are defined in relation to the trial objectives. Efficacy endpoints will be evaluated using the SAF. Further analyses will be defined in the SAP.

Efficacy will be determined from the number of subjects with CR, PR, SD or PD, according to iRECIST based on the investigator's assessments. PFS (percentage of subjects alive and progression-free after trial treatment start) will also be determined. These clinical response data will be summarized.

ORR (proportion of subjects with a best overall response of PR or, CR) will be evaluated based on iRECIST.

For Phase I Cohort 3 and all Phase IIa arms, ORR (proportion of subjects with a best overall response of PR or, CR) will be evaluated by two additional approaches based on itRECIST:

- Injected response: considering only the targeted-injected lesions.
- Non-injected response: considering only the targeted-non-injected lesions.

8.1.5 Pharmacokinetic Analysis (PK)

The first 9 subjects of Phase I, all subjects of Arm C, and the first 12 subjects of Arm D who have received CyPep-1 and have provided one evaluable pre-dose and at least one post-dose PK blood sample will be evaluable for PK (CyPep-1 PK Analysis Set).

PK analysis is planned via the determination of the plasma concentration time profile of CyPep-1 and, if detectable plasma drug levels are identified, the derived PK parameters will be assessed. These include area under the curve (AUC), peak plasma concentration (C_{max}), time to reach C_{max} (t_{max}), systemic clearance (CL), elimination half-life ($t_{1/2}$) and volume of distribution (VD).

8.1.6 Immunological Analysis

[figure not shown]
This analysis will be performed on the SAF.

The relative change in intratumoral CD8+ T-cell infiltration (CD8+ expression) in the biopsied injected, and whenever available, non-injected lesions between screening and Week 6 will be assessed.

The association between the relative changes in CD8+ T-cell infiltration and response rate in the injected lesions (per itRECIST) and all lesions (per iRECIST) will be assessed.

The change in T-cell receptor (TCR) clonality levels will be assessed in the available peripheral blood samples. To assess the hypothesis that CyPep-1 increases TCR clonality systematically, which suggests that T-cells are targeting the tumor, the clonality diversity metric will be computed for all subjects providing peripheral blood samples at screening and/or Week 6 of every CyPep-1 treatment cycle. Based on preliminary on file data of TCR clonality analysis in peripheral blood dated Nov 2022, the dataset collected is sufficient for the intended analysis and further sampling will provide no additional insights. Uncertainty about the representativeness of data generated with blood samples regarding TCR changes in the tumor microenvironment has lead Cytovation to reconsider this scientific relevance of this assay. Therefore, Cytovation decided to stop collecting blood samples for TCR clonality analysis. TCR sequencing might be performed on the available remaining tumor biopsy material from the analyses of changes in the tumor microenvironment. Overlaps of T cell clones in respect to expansion and breadth of T cell clonality before and after intratumoral injection with CyPep-1, as monotherapy and in combination with pembrolizumab (central analysis) will be analyzed.

The change in tumor microenvironment will be examined via the expression of selected candidate immune markers by immunohistochemistry: [REDACTED]

For each marker, a difference in expression will be explored.

Changes in cytokine levels (only for Arms A, B, and C) and in frequency of various immune cell types in peripheral blood (immunophenotyping) will be explored.

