2.2.3 Exploratory Endpoints

The exploratory endpoints are:

- For all Phase IIa arms: ORR in injected lesions and non-injected lesions, separately, per itRECIST* [[Goldmacher 2020](#)]).
- Progression-free survival (PFS) per iRECIST based on the investigator's assessment.
- Overall survival (OS).
- The relative change in number of tumor infiltrating CD8+ T-cells in the injected and, whenever available, non-injected tumor biopsies.
- The association between the relative change in tumor infiltrating CD8+ T-cells and response rate in the injected lesions (per itRECIST) and all lesions (per iRECIST). The change in T-cell receptor (TCR) clonality levels in peripheral blood and (when available) biopsied lesions.
- Changes in the tumor microenvironment (injected and, whenever available, non-injected tumor biopsies) via expression of selected candidate immune markers:
[REDACTED]
[REDACTED]
[REDACTED]
- For Arms A, B, and C: [REDACTED]
[REDACTED]
- Peripheral blood phenotyping of selected immune cell markers.

[figure not shown]
*itRECIST will be programatically calculated using data obtained from iRECIST assessments following the itRECIST principle summarized in [Appendix F Figure 1](#).

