4.3 Changes from and Additions to the Clinical Study Protocol

The following additions to the Clinical Study Protocol were made in this SAP:

1. Characterization of potential hepatotoxicity was added.
2. Markedly abnormal criteria for vital signs added.
3. Section for Other exploratory analyses was added (including analyses of PK and toxicity and intratumoral dose concentration).
4. Sections on visit alignment were added.
5. itRECIST analyses for Phase I cohorts were added.
6. Analyses of overall survival by RMH and GRIM-scores and including/excluding subjects with adrenocortical carcinoma were added.

The following changes from Clinical Study Protocol were made in this SAP:

Not applicable, no discrepancies between SAP and Clinical Study Protocol.

5 Trial Objectives and Endpoints

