5.2.3 Exploratory Endpoints

- For all Phase IIa arms: ORR in injected lesions and non-injected lesions, separately, per itRECIST* (Intratumoral Response Evaluation Criteria in Solid Tumors) (Goldmacher, 2020).
- Progression-free survival (PFS) per iRECIST based on investigator's assessment.
- Overall survival (OS).
- The relative change in number of tumor infiltrating CD8+ T-cells in the injected and, whenever available, non-injected tumor biopsies.
- The association between the relative change in tumor infiltrating CD8+ T-cells and response rate in the injected lesions (per itRECIST) and all lesions (per iRECIST). The change in T-cell receptor (TCR) clonality levels in peripheral blood and (when available) biopsied lesions.
- Changes in the tumor microenvironment (injected and, whenever available, non-injected tumor biopsies) via expression of selected candidate immune markers:
[REDACTED]
- For Arms A, B, and C: changes in the levels of peripheral blood cytokines ([REDACTED]
[REDACTED])
- Peripheral blood phenotyping of selected immune cell markers.

*itRECIST will be programmatically calculated using data obtained from iRECIST assessments following the itRECIST principle summarized in Clinical Study Protocol Appendix F Figure 1.

Statistical Analysis Plan

SMS-0571/CyPep-1

V3.0 Final

[figure not shown]
04-Jun-2024

6 Study Methods

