10.2.4 Immunological Parameters

Immunological parameters will be analyzed using the SAF.

CD8+ T-cell Infiltration

CD8+ data are provided to [REDACTED]; details on data transfer are specified in corresponding *External Data Transfer Agreement*.

CellCarta is responsible for providing CD8+ T-cell infiltration data summaries to sponsor in accordance with the study protocol.

For this SAP, CD8+ T-cell infiltration data will only be listed.

T-cell Receptor Clonality Levels

TCR clonality data are provided to [REDACTED] via the Immunoseq tool.

Adaptive is responsible for providing T-cell receptor clonality levels data summaries to sponsor in accordance with the study protocol.

However, Simpson's clonality results in biopsy on Cycle 1 Visit 4 will be correlated to Simpson's clonality results in blood on Cycle 1 Visit 4 for the 6 subjects who had TCR data measured in both biopsy and blood. Scatter plot will be used for this analysis. Results will be displayed in pooled fashion (i.e., no presentation by cohort/arm) due to small sample size.

T-cell receptor clonality levels data will also be listed.

Tumor Microenvironment

Tumor microenvironment data are provided to [REDACTED]; details on data transfers are specified in corresponding *External Data Transfer Agreements*.

[REDACTED] are responsible for providing tumor microenvironment data summaries to sponsor in accordance with the study protocol.

However, PD-L1 expression data (Tumor Positive Score) will be presented by summary statistics for Arm B subjects at baseline in scope of this SAP.

For this SAP, tumor microenvironment data will only be listed.

Cytokine Levels

Cytokines data are provided to [REDACTED]; details on data transfer are specified in corresponding *External Data Transfer Agreement*.

Changes in cytokine levels (only for Arms A, B, and C) will be explored. [REDACTED].

The change in cytokine levels between screening and post-baseline timepoints will be assessed and estimated using paired t-tests with a 0.05 significance level. In addition to test results, the summary table will include summary statistics for cytokine levels by timepoint and for change from screening to each post-baseline timepoint.

Cytokines data will also be listed.

Peripheral Blood Phenotyping

Peripheral blood phenotyping data are provided to [REDACTED]; details on data transfer are specified in corresponding *External Data Transfer Agreement*.

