Cerba Research is responsible for providing peripheral blood phenotyping data summaries to sponsor in accordance with the study protocol.

For this SAP, peripheral blood phenotyping data will only be listed.

Exploratory Analyses of Immunological Parameters

Correlation between immunological parameters and select efficacy endpoints may be explored in case immunological signals are observed. Such analyses, if carried out, will be described in an SAP amendment or in the Clinical Study Report, as applicable.

Statistical Analysis Plan

SMS-0571/CyPep-1
V3.0 Final
04-Jun-2024

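### The CD8–response association is a named exploratory endpoint, but the SAP plans no analysis of it and leaves any such analysis to an undefined signal

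*Protocol*

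**What the plan says.** Protocol 2.2.3 lists as an exploratory endpoint "The association between the relative change in tumor infiltrating CD8+ T-cells and response rate in the injected lesions (per itRECIST") and in all lesions by iRECIST. Protocol 8.1.6 turns this into an analysis commitment: the association between "relative changes in CD8+ T-cell infiltration and response rate in the injected lesions (per itRECIST) and all lesions (per iRECIST) will be assessed". SAP 5.2.3 keeps the endpoint: "The association between the relative change in tumor infiltrating CD8+ T-cells and response rate in the injected lesions".

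SAP 10.2.4 then says three things that bear on it:

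- On CD8 itself: "For this SAP, CD8+ T-cell infiltration data will only be listed".
- On the external laboratory, which is to provide "CD8+ T-cell infiltration data summaries to sponsor in accordance with the study protocol".
- On linking markers to efficacy: "Correlation between immunological parameters and select efficacy endpoints may be explored in case immunological signals are observed". The next sentence adds: "Such analyses, if carried out, will be described in an SAP amendment or in the Clinical Study Report, as applicable".

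On changes from the protocol, SAP 4.3 states: "Not applicable, no discrepancies between SAP and Clinical Study Protocol".

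**The concern.** An unconditional protocol analysis has become an optional one in the SAP. The SAP does not define what counts as a signal or which efficacy endpoints would be selected. It gives no effect measure, test, analysis population or rule for missing biopsies. The method may be described for the first time in the clinical study report.

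Two things are at stake. First, the endpoint may get no output at all, while the SAP still lists it and reports no change. Second, whether it is analysed can depend on what has been seen. The trial is open-label (Protocol 3.2). SAP V3.0, dated 04 June 2024, followed a mid-study analysis in summer 2023 that covered all data to its cut-off (SAP 7.1), and SAP 1.1 gives sponsor comments on that analysis as the reason for the revision. The documents do not say whether CD8 results were examined then.

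**Working it through.** There is no stated figure to reproduce. The check is mainly a comparison of the two documents.

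1. **The ingredients.** The association needs a CD8 change and a response for each subject.
   - CD8 change: summaries by the laboratory and a listing (SAP 10.2.4).
   - Injected-lesion response: derived by program under this SAP (SAP 10.2.1 and Appendix 5).
   - All-lesion best overall response: derived under this SAP (SAP 10.1.1).
   - The link between them: nothing planned.

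2. **Is it placed elsewhere in the SAP?** SAP 10.2.5 covers two possible subgroup analyses (weekly versus Q2W dosing, and Arm D subjects meeting inclusion criterion 8e). SAP 10.2.6 covers adverse events by detectable Cmax, intratumoral dose concentration by best overall response, and injected-lesion volume against itRECIST response. None uses CD8.

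3. **Where did the protocol expect it?** Protocol 8.1.9 says exploratory analyses will be specified in the SAP. Protocol 8.1 says changes known when the SAP is prepared will be described there. SAP 4.3 lists six additions and no changes.

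4. **Do small numbers or exploratory status explain the gap?** The SAP plans, without condition, a Fisher's exact test of lesion volume against injected response (10.2.6) and a scatter plot of TCR clonality in biopsy against blood for 6 subjects (10.2.4). Neither analysis is named in the protocol's endpoint list. The CD8 association is.

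5. **Can the bias be sized?** Only by assuming a trigger. I simulated 100,000 samples of 15 pairs (an assumed number) with no true association:

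| Assumed trigger for running the analysis | Mean correlation when it is run |
|---|---|
| Correlation is positive | 0.22 |
| Correlation is in its top quarter | 0.34 |
| Mean CD8 change is significant (two-sided 5%) | about 0.00 (−0.004), with a 5% test of the correlation still rejecting 5.0% of the time |

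   The answer runs from none to 0.34 according to a rule that the SAP does not give.

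6. **How informative is binary response?** With r responders among n subjects, the smallest two-sided exact rank-sum p is 2/C(n, r), where C(n, r) counts the ways of choosing r from n. The number of pairs is not stated, so I take a range. For one responder it is 2/n: 2/10 = 0.20, 2/15 = 0.13, 2/30 = 0.07. For two responders in 15 it is 2/105 = 0.019. With a single responder, a binary comparison cannot reach 5% until n = 40 (2/40 = 0.05). That supports adding a continuous measure of tumour change.

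**The case against.** The strongest reply is delegation. The laboratory's summaries are to follow the protocol, and the same protocol section contains the association, so the laboratory's own plan may cover it. That plan is not among the documents, and the SAP does not say the laboratory supplies summaries alone. This stands as a possibility. However, the delegation names CD8 data, injected response is derived under this SAP, and no text provides for sending response data to the laboratory.

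The endpoint is also one exploratory item in a non-randomised proof-of-concept trial. The hypothesis of turning cold tumours hot is addressed by separate endpoints as well: relative CD8 change and microenvironment markers. That stands, and it limits the weight of the point. Protocol 8.4 further allows deviations from the original SAP to be described in a revised SAP or the final report. That covers reporting a deviation; it does not make the statement in SAP 4.3 accurate.

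A reader might go further and infer any of three things that the documents do not support:

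- **That the endpoint has been dropped and a null result will never be reported.** SAP 5.2.3 keeps the endpoint, and the wording of SAP 10.2.4 is permissive and does not bar a null result. CD8 data and best overall response are both listed, so the all-lesion association could be reconstructed subject by subject. A listing is still not an analysis.
- **That any reported association is biased by a known amount.** The natural reading of an immunological signal is a change in a marker. Selecting on that alone leaves the correlation with an independent response unbiased, as the third row of the table shows. The values 0.22 and 0.34 require someone to look at the association before deciding to run it.
- **That screening several markers makes a false signal likely.** With 5 to 15 independent null markers at 5%, 1 − 0.95^5 = 23% and 1 − 0.95^15 = 54%. The panel size, independence and threshold are all assumed, and the figure says nothing about CD8, the one marker named in this endpoint.

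**Conclusion.** The mismatch is real and should be corrected. Protocol 2.2.3, Protocol 8.1.6 and SAP 5.2.3 name the association. SAP 10.2.4 gives it no planned analysis and makes any marker–efficacy correlation depend on an undefined trigger. SAP 4.3 says nothing has changed. The consequence is that a stated endpoint may go unanalysed, or may be analysed at discretion after data have been seen.

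Selective reporting is a risk created by the undefined trigger and is not an established fact. Its size cannot be quantified from the documents. Primary and secondary conclusions are unaffected. The conclusion assumes that no separate plan, such as the laboratory's, already specifies the association; if one does, the defect reduces to a missing cross-reference.

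**What to change.** In SAP 10.2.4:

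- Remove the signal condition for CD8.
- State that, for every SAF subject with paired screening and Week 6 biopsies of an injected lesion, relative CD8 change will be presented against best injected response (itRECIST) and against best overall response (iRECIST).
- Because responders may be few, add a scatter plot and Spearman correlation with 95% confidence interval against best percentage change in sum of diameters, for injected target lesions and for all target lesions. Both quantities are already derived (SAP 10.1.1 and Appendix 5).
- Report all of this whatever the result, with the number of paired subjects.
- Label any other marker–efficacy correlation post hoc.

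If the laboratory's plan already contains the association, cite it in SAP 10.2.4. If the sponsor does not intend to analyse the endpoint, declare and justify that in SAP 4.3.

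The cost is SAP wording and a small amount of extra output from data that the SAP already lists or derives. The downside is that a null or imprecise result will have to be shown.

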8.1.7 Concomitant Treatment

Concomitant medication and concomitant therapy will be summarized as number of subjects being treated with each type of medication/therapy classified according to Anatomical Therapeutic Chemical (ATC) level 2 and World Health Organization (WHO) Drug Dictionary preferred term. The SAF will be used for this presentation.

8.1.8 Tabulation of Individual Participant Data

Individual participant data will be listed by measure and time point.

8.1.9 Exploratory Analyses

Exploratory analyses will be specified in the SAP. A separate analysis of subjects having received weekly vs Q2W CyPep-1 administration is planned as sub-group analysis.

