For Phase I and Phase IIa, Arms A, B and C, CyPep-1 will be administered intratumorally Q2W, on Day 1, 15, and 29 of each cycle. In the absence of DLT/TLTs during Cycle 1, treatment continues with Q2W IT injections of CyPep-1. For Arm D, CyPep-1 will be administered intratumorally QW until the second iRECIST/itRECIST assessment at week 16, followed by a Q2W dosing scheme. For all phases/arms, treatment will continue until confirmed PD, unacceptable toxicity, death, or consent withdrawal, loss to follow up, or trial end, whichever occurs first (for discontinuation refer to Section 4.3.1).

Administration will be through a needle inserted trans-dermally. The needle should be redirected along multiple tracks to ensure even dispersion of CyPep-1 throughout the lesion. For Arm C, CyPep-1 will be administered via intralesional injection with ultrasound guidance into one metastatic liver lesion. A detailed guidance for intratumoral administration of CyPep-1 is presented in the Study Procedural Manual.

The CyPep-1 concentration for each dose cohort during dose escalation (Phase I) is as follows:

Dose cohort	CyPep-1 concentration
1	0.5 mg/mL
2	2 mg/mL
3	5 mg/mL

The total amount of CyPep-1 injected will depend on the tumor volume(s). Effort should be made to administer the maximum planned injection volume of CyPep-1 as planned per lesion size.

CyPep-1 Injection Volume:

The volume delivered to each lesion selected for injection will be determined based on the longest diameter measured by the most accurate measurement technique available for each lesion (e.g. caliper, CT, or MRI) at screening and every 8 weeks during the iRECIST/itRECIST assessments. A chosen technique used at screening will be consistently used throughout the study. Lesion sizes need to be checked before each injection by either caliper (mandatory for Arm D and to-be-injected cutaneous/subcutaneous lesions for Phase IIa Arms A and B) or other imaging modalities used to guide CyPep-1 injections, i.e. ultrasound, CT, or MRI. For Arm C, the lesion size measurement will be performed by the same imaging modality used to guide CyPep-1 injections. To ensure consistency of the measurements, the sites need to strive for having the same operator to perform all measurement for a chosen measuring technique. If there are major changes in the lesion size, the injection volume may be adjusted based on the ultrasound measurements per investigator's opinion and consultation with the Medical Monitor is possible.

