For Phase IIa Arms A and B, for a lesion > 7 cm, the same lesion should be considered to be injected weekly with up to 4 mL of CyPep-1 for the first 6 weeks (on Day 1, 8, 15, 22, 29 and 36), independent of the potential change in lesion size, followed by Q2W 4 mL administrations of CyPep-1. The visits on Days 1, 15, 29 and 36 will follow the assessments as per schedule. The visits on Days 8 and 22 will follow the assessments as per D15 (C1V2; excluding central lab sampling for cytokine analysis and blood sampling for immune cell phenotyping).

For Phase IIa Arm D, the to-be-injected volume for injection is preferably divided over as many lesions as possible. The longest diameter of the lesions for injection is ideally smaller than 2 cm and should not exceed 5 cm.

For subjects in Arms A, B and C, the injection volume will be:

Measured Lesion Diameter (cm)	Injected volume (mL)
≤ 1	1
> 1 and ≤ 2	2
> 2	4

For subjects in Arm D, the injection volume will be:

Measured Lesion Diameter (cm)	Injected volume (mL)
≤ 0.79	0.1
0.80 to 0.99	0.2
1.00 to 1.24	0.5
1.25 to 1.50	1.5
1.51 to 2.49	3.0
≥ 2.50	4.0

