10.2.5 Exploratory Subgroup Analyses

The following sub-group analyses may be carried out:

1. Analysis of subjects having received weekly vs Q2W CyPep-1 administration,
2. Analysis of subjects in Arm D corresponding to Inclusion Criteria 8e,

Analysis of subjects having received weekly vs Q2W CyPep-1 administration

Comparisons of efficacy data between subjects who received weekly and by-weekly CyPep-1 administrations may be carried out, given sufficient sample size in both groups. No such analyses are planned for this version of SAP.

Analysis of subjects in Arm D corresponding to Inclusion Criteria 8e

Exploratory analyses of subjects in Arm D corresponding to Inclusion Criteria 8e may be carried out. No such analyses are planned for this version of SAP.

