10.2.6 Other Exploratory Analyses

Pharmacokinetics and Toxicity

A summary table of AEs (by SOC and PT) by cycle and cohort will be created for the PKS, split by C_{max} detectable vs not detectable.

Intratumoral Dose Concentration

Summary statistics for intratumoral dose concentration at baseline (mg/mm^3) will be presented by best overall response per iRECIST (iSD and better vs worse than iSD) and cohort/arm for the SAF. Corresponding box plots will also be created.

Intratumoral dose concentration at baseline will be calculated following the steps below:

1. For each subject, the volume of i th lesion injected at first treatment administration will be estimated using the formula of volume of sphere:

$$V_i = \frac{1}{6} \cdot \pi \cdot d_i^3$$

where d_i is the longest diameter of lesion i obtained by baseline CT scan (if CT scan is not available, then results from local measurements performed before treatment injection will be used).

2. For each subject, the intratumoral dose concentration at baseline will be calculated as:

$$Conc_{IT} = Average \left(\frac{D_i}{V_i} \right)$$

where D_i is the dose injected (mg) into i th lesion at first treatment administration and average is taken over all lesions injected at first treatment administration.

Injected Target Lesion Volume and Best Response in Injected Target Lesions per itRECIST

Injected target lesion volume is hypothesized to be correlated with injected target lesion response per itRECIST. In order to explore that relationship, the following analysis steps will be taken:

1. For each subject, the injected target lesions volume (mm^3) at baseline will be calculated as sum of volumes of all target lesions injected at baseline, based on the formula of volume of sphere:

$$V = \sum_i \frac{1}{6} \cdot \pi \cdot d_i^3$$

where d_i is the longest diameter of lesion i obtained by baseline CT scan (if CT scan is not available, then results from local measurements performed before treatment injection will be used). For this calculation, baseline can differ between different injected target lesions of the same subject following the itRECIST rules provided in [APPENDIX 5. itRECIST DERIVATION RULES](#).

2. Then, median of injected target lesion volume over all patients in SAF will be calculated and patients will be divided into two groups: low volume (\leq median) and high volume ($>$ median).

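### The protocol plans a weekly versus two-weekly analysis that the SAP leaves out without declaring it, and the Cycle 1 safety summaries mix the two schedules

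*Protocol*

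**What the plan says.** **The commitment.** Protocol 8.1.9 states: "A separate analysis of subjects having received weekly vs Q2W CyPep-1 administration is planned as sub-group analysis". It does not limit the analysis to efficacy, and it does not mention safety. Protocol 8.1 requires that changes already known when the SAP is prepared be described in the SAP.

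**The SAP.** Section 10.2.5 says: "Comparisons of efficacy data between subjects who received weekly and by-weekly CyPep-1 administrations may be carried out, given sufficient sample size in both groups". It then adds: "No such analyses are planned for this version of SAP". Section 4.3, on changes from the protocol, reads: "Not applicable, no discrepancies between SAP and Clinical Study Protocol".

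**The two schedules.** For Phase I and Arms A, B and C, the protocol synopsis (Treatment Regimens) gives the standard schedule: "CyPep-1 will be administered intratumorally Q2W, on Day 1, 15, and 29 of each cycle". For a lesion over 7 cm in Arms A and B, Protocol 5.3.1.2 says "the same lesion should be considered to be injected weekly with up to 4 mL of CyPep-1 for the first 6 weeks", with injections on Days 1, 8, 15, 22, 29 and 36. Protocol 5.3.4 extends the same option to Arm C.

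**The safety tables.** Type and number of AEs, DLTs and TLTs are primary endpoints (Protocol 2.2.1). SAP 11.1.3 presents AEs for each cohort or arm and in total. Weekly subjects are identified in SAP 9.6.1, but only to be counted in the exposure table.

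**The concern.** A sub-group analysis that the protocol calls planned is not in the final SAP, and the SAP says that nothing has changed. Someone reading the report against the protocol would look for it and find neither the analysis nor a reason for its absence.

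The consequence is larger for safety than for efficacy. The Phase I cohorts behind the recommended dose were scheduled every two weeks. If some Arm A or Arm B subjects were dosed weekly, the arm's Cycle 1 AE, DLT or TLT rate averages two exposures and describes neither. If efficacy were later compared by schedule, the weekly group would consist of subjects with very large lesions whom the investigator chose to treat more often. SAP 10.2.6 itself says "Injected target lesion volume is hypothesized to be correlated with injected target lesion response per itRECIST".

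**Working it through.** **1. The plan's own figure.** Protocol 5.3.1.2 caps the volume at 4 mL per treatment day and states the matching dose as 20 mg. At 5 mg/mL, 4 × 5 = 20 mg, so it reproduces. Neither document gives a sample size or precision for the schedule comparison.

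**2. Cycle 1 exposure** = injections × mL per visit × 5 mg/mL. Two-weekly volumes are from the Arm A, B and C table in Protocol 5.3.1.2, for a single injected lesion.

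| Schedule | Calculation | Cycle 1 dose | Weekly ÷ this |
|---|---|---|---|
| Weekly, full 4 mL | 6 × 4 × 5 | 120 mg | – |
| Two-weekly, lesion > 2 cm | 3 × 4 × 5 | 60 mg | 2 |
| Two-weekly, lesion > 1 to 2 cm | 3 × 2 × 5 | 30 mg | 4 |
| Two-weekly, lesion ≤ 1 cm | 3 × 1 × 5 | 15 mg | 8 |

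The weekly volume has an upper limit rather than a fixed value, so 120 mg is a maximum. Injecting several lesions can also bring a two-weekly subject to 4 mL.

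**3. Where schedule appears in the safety output.**
- SAP 11.1.3: no AE, DLT or TLT summary is split by schedule.
- SAP 9.6.1: one line counts the weekly subjects.
- SAP 10.2.6: the only AE table by cycle uses the PK set, which SAP 7.2.3 restricts to the first 9 Phase I subjects, Arm C and Arm D. Arms A and B are outside it.
- SAP 8.10: selected tables combine Cohort 3 with Arm A, adding the six Cohort 3 subjects from Phase I to an arm that allows weekly dosing.

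**4. A TLT criterion that depends on schedule.** In Arm B, missing more than 25% of Cycle 1 CyPep-1 doses through drug-related AEs is a TLT (Protocol 3.1.2). One missed dose is 1/3 = 33% on the two-weekly schedule and 1/6 = 17% on the weekly one. The same event counts under this criterion on one schedule and not on the other.

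**5. The weekly flag.** SAP 9.6.1 calls a subject weekly if the second dose came no more than one week after the first. The nominal Day 8 dose is exactly 7 days after Day 1. Footnote 19 of the schedule of assessments refers the Day 8 visit to the Day 15 assessments, whose window is ±3 days. If that window applies, the dose may fall as late as Day 11, an interval of 10 days, and Days 9 to 11 all fail the definition. The earliest two-weekly second dose is Day 12 (11 days), so window error runs one way: weekly subjects are counted as two-weekly. A subject with only one dose can never be flagged.

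**6. Scale, by assumption only.** Take 33 subjects (18 in Arm A plus 15 in Arm B), 3 to 8 of them weekly, with an event risk of 40% weekly and 10% two-weekly. None of the weekly counts or risks is in the documents, and the SAP shows the two arms separately.
- Pooled rate with 3 weekly: (3 × 0.4 + 30 × 0.1)/33 = 12.7%. With 8 weekly: (8 × 0.4 + 25 × 0.1)/33 = 17.3%.
- Power of a two-sided Fisher test at 5%: 18% (3 weekly), 27% (5) and 42% (8).
- With no events in the weekly group, the upper 95% Clopper-Pearson limit is 71% (n = 3), 52% (n = 5) or 37% (n = 8).

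A fourfold difference in risk could sit inside an unremarkable pooled rate. A formal test would not be informative, but a descriptive split with exact intervals is feasible.

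**The case against.** The strongest reply is that the protocol never promised a safety split. Section 8.1.9 sits under exploratory analyses and leaves the detail to the SAP. The exploratory objectives (Protocol 2.1.3) concern efficacy, survival and immune effects. This stands: a safety split by schedule is a recommendation, not a broken commitment. It does not excuse dropping the analysis altogether while declaring no change.

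A reader might infer that the weekly safety data are hidden. They are not. SAP 11.1.3 lists all AEs, DLTs and TLTs by subject, and SAP 9.6.1 lists exposure. The aligned visits in SAP Appendix 4 keep Day 8 and Day 22 rows, so some weekly-only laboratory and vital-sign data appear separately. The Dose Escalation Committee analyses are in a separate plan (SAP 7.3) and may be split by schedule. What is missing is any summary table.

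A reader might also infer that the SAP plans an unadjusted, confounded efficacy comparison. It plans none and states no method. It calls volume and response correlated, which is not a claim that volume drives response. Weekly dosing is only to be considered for a lesion over 7 cm, so size does not fully determine schedule. Restricting a comparison to such lesions would still leave investigator choice.

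**Conclusion.** The concern holds in a limited form. There is a plain, undeclared mismatch between Protocol 8.1.9 and SAP 10.2.5, and the statement in SAP 4.3 is wrong on this point. The planned AE, DLT and TLT summaries for the affected arms can mix subjects with up to 6 and with 3 Cycle 1 injections, at most 120 mg and at most 60 mg. The ratio of 2 is exact for scheduled injections and for dose at full volume.

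The effect on reported rates cannot be sized, because the number of weekly subjects is not stated. The documents do not support reading the doubled exposure as a doubled event risk. If each injection carried an independent risk of 5%, 10% or 20%, the formula 1 − (1 − p)^k would give Cycle 1 incidences of 14%, 27% or 49% for k = 3, and 26%, 47% or 74% for k = 6. Those risks are assumptions, and independence is doubtful because premedication and dosing depend on earlier reactions.

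The size contrast depends equally on the comparator. On the SAP's sphere formula a 7 cm lesion (180 cm³) is 43 times the volume of a 2 cm lesion (4.2 cm³), but only (7/5)³ = 2.7 times a 5 cm lesion.

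**What to change.** 1. **SAP 10.2.5.** Replace the statement that nothing is planned with descriptive Cycle 1 tables by schedule received, within each arm where weekly dosing occurred: TEAEs, CyPep-1-related TEAEs, Grade ≥ 3 TEAEs, and DLTs (TLTs in Arm B). Show number of injections, mg received and baseline lesion size, with no formal test. If the sponsor prefers not to, declare the omission and its reason in SAP 4.3. Keep the single Arm D subject, who is weekly by design, in that arm's own column.
2. **SAP 9.6.1.** Define schedule received from all Cycle 1 doses, for example any injection at a nominal Day 8, 22 or 36 visit. Show subjects with only one injection as a separate row, so that early stoppers do not fall into the two-weekly group by default.
3. **Efficacy.** If shown by schedule, keep it descriptive, show lesion size, and state that differences are confounded by lesion size and investigator choice and cannot be attributed to schedule.
4. **Protocol.** Section 5.3.1.2 (Arms A and B) and Section 5.3.4 (Arms A, B and C) disagree on which arms may receive weekly dosing. They must be reconciled, so that the tables cover every affected arm.

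**Cost:** SAP wording, one revised derivation and a split of existing tables. No new data are collected. The subgroups will be small, which limits the tables to description.
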